## **11.0 STATISTICAL PRINCIPLES**

### **Levels of confidence and p-values**

A double-sided p-value of  $< 0.05$  will be considered statistically significant. 95% confidence intervals will be provided.

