For the trained immunity analyses, 15 participants from each group will have extra blood samples taken on day 0, 14, and 42. Peripheral blood mononuclear cells (PBMCs) are isolated from the samples and subsequently stimulated in vitro with various antigens. The immune function will be assessed by cytokine production capacity measured by Luminex technology after stimulation. The outcome measure for this analysis is concentration of different types of cytokines produced following stimulations. We will compare fold change in cytokine production between the groups at the various timepoints with and without adjustment for responses in control medium. This will allow us to determine whether BCG in the different combinations with influenza vaccine induces trained immunity in this population.

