**List of variables:**

Variable name	Definition	Type	Scale
Primary outcome: Change in antibody levels to influenza virus strains included in the IIV, comparing levels at day 14 and day 42.			
ab_diff_strain	Influenza antibody titer (GMT) day 42 minus day 14. For each strain.	Continuous	<20 to 320
seroconv	Seroconverted after influenza vaccination (4-fold increase in Ab titer). For each strain.	Binary	0: no 1: yes
Secondary outcome, self-reported infections:			
infection	Infection or symptoms consistent with infection (0 or 1 every survey period).	Binary	0: no 1: yes
Secondary exposure:			
ab_day42_cat	Influenza ab titer day 42 (GMT). Secondary exposure.	Categorical	1. quartile 2. quartile 3. quartile 4. quartile
Secondary outcome, immunological:			
b_lymph	Number of activated B-cells. For all relevant subtypes.	Continuous	0.0-0.3 x 10  /L

cytokine_stim_day	Cytokine concentration (TNF $\alpha$ , IL-1 $\beta$ , IFN- $\gamma$ ) after stimulation with: Poly(I:C), Pam3CSK4, LPS, and influenza vaccine at the various timepoints (day 0, 14, and 42).	Continuous	0-1500 pg/mL
diff_cytokine_stim_day	Fold change in cytokine concentration from baseline value (day 0) to day 14 and 42 after stimulation with various stimuli. Compared between the randomization groups. Using randomization group as exposure (categorical).	Continuous	0-10

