#### Secondary outcomes:

##### *Self-reported infections:*

The hazard ratio of infections will be estimated using an Andersen-Gill Cox proportional hazards regression model with infections included as recurrent events and time since inclusion as underlying time scale. The proportional hazards assumption will be tested using Schoenfeld residuals. As participants are only able to report one infectious episode during a follow-up questionnaire, the event will be assigned to the first day within the questionnaire period, and the following 14 days of follow-up excluded for analyses as it represents risk free time.

Association between influenza antibody titer level at day 42 and rate of infections will also be explored in Andersen-Gill Cox proportional hazards regression model, using antibody titer at day 42 as exposure and self-reported infections after day 42 as outcome. Antibody titers will be categorized into quartiles or similar relevant categories. The analysis will be adjusted for sex and age group.

Absolute risk reduction will be calculated using Cox regression.

*Immunological outcomes (subgroup analyses):*

Mean change in number of activated B-cells, concentration of cytokines, as well as fold change in cytokine concentration after stimulation from day 0 to day 14 and from day 14 to day 42 will be compared between the control group and the three treatment groups in linear regression analyses. With and without adjustment for responses in the control condition.

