### Figure 3: Results trained immunity.

Boxplots showing fold increase in cytokine production after stimulation with bacterial antigens and influenza vaccine at day 0, day 14, and day 42 for each treatment group.

\* Denotes within-group statistically significant change in cytokine levels between day 0 and 14 or between day 14 and 42

Δ Denotes between group statistically significant different change in cytokine levels between day 0 and 14 or between day 14 and 42

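### The Part B trained-immunity analysis marks up to 48 BCG comparisons at 0.05 each, with no correction or decision rule, yet says it will determine whether BCG induces trained immunity

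*SAP*

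**What the plan says.** Part B, section 13.0 (Secondary outcomes) takes extra samples on days 0, 14 and 42 from 15 participants in each of the four groups and measures cytokine production after in vitro stimulation. It closes with: "This will allow us to determine whether BCG in the different combinations with influenza vaccine induces trained immunity in this population". Hypothesis (b) in the Part B objectives, that BCG acts partly through innate immune memory, is among the hypotheses the trial says it will test.

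The list of variables in section 13.0 names three cytokines (TNF-alpha, IL-1beta and IFN-gamma), measured "after stimulation with: Poly(I:C), Pam3CSK4, LPS, and influenza vaccine at the various timepoints (day 0, 14, and 42"). Section 14.0 (Immunological outcomes) compares "fold change in cytokine concentration after stimulation from day 0 to day 14 and from day 14 to day 42" between control and each of the three treatment groups by linear regression, and adds: "With and without adjustment for responses in the control condition".

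Section 11.0 sets one threshold for all of Part B: "A double-sided p-value of $< 0.05$ will be considered statistically significant". The legend of Figure 3 in section 15.0 gives significant group differences their own symbol: "Denotes between group statistically significant different change in cytokine levels between day 0 and 14 or between day 14 and 42".

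No cytokine, stimulus, window, contrast or adjustment version is named as the deciding one. No correction is stated, and nothing says how many marks would amount to trained immunity. The analysis is headed as a secondary outcome in a subgroup. It is not labelled exploratory, although Part A section 7.0 does use that label for another analysis.

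**The concern.** A sentence promising to determine whether an effect exists needs a rule that turns results into an answer. Here there is a grid of tests, each at 5%, and a figure that marks every one that crosses the line. In a subset this small, some cells are likely to be marked by chance. A reader of Figure 3 then has no pre-stated way to tell a chance mark from evidence for hypothesis (b), and the authors have no pre-stated way to decline to interpret one. At stake is the mechanistic conclusion of Part B. The antibody primary outcome is not affected.

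**Working it through.** **Inputs.** From the SAP: 3 cytokines and 4 stimuli (section 13.0, list of variables); 2 windows and 3 contrasts with control (section 14.0); two-sided 0.05 per test (section 11.0); 15 participants in each of 4 groups (section 13.0). The correlation between readouts is not given, so it is an assumption and a range is shown. The SAP states no test count or error rate for this analysis, so there is no figure to reproduce.

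**Count.** 3 × 4 = 12 readouts. 12 × 2 windows × 3 contrasts = 72 between-group tests of fold change per adjustment version.

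**Which of these contain BCG.** In the vaccination schedule in section 10.0, only group 1 receives BCG on day 0. Group 3 receives placebo and group 4 influenza vaccine on day 0, and both receive BCG on day 14.

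- Day 0–14, group 1 versus control: 12 tests with BCG.
- Day 0–14, groups 3 and 4 versus control: 2 × 12 = 24 tests without BCG. Group 3 versus control is placebo against placebo, and group 4 versus control differs only by influenza vaccine.
- Later window, groups 1, 3 and 4 versus control: 3 × 12 = 36 tests with BCG.

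Tests that can bear on BCG: 12 + 36 = 48.

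**Expected false marks under no effect.** 48 × 0.05 = 2.4, whatever the correlation.

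**Chance of at least one false mark.** If the 48 tests were independent: 1 − 0.95^48 = 0.915. They are not, since they share a control group, a day-14 sample and participants. I therefore used simulation: 15 per group, no effect in any arm, 12 readouts with common correlation r, and pooled-variance t tests with 4 × 14 = 56 degrees of freedom, on one adjustment version.

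| Assumed r | Any mark among the 48 | Any increase among the 48 |
|---|---|---|
| 0 | 88% | 66% |
| 0.3 | 82% | 56% |
| 0.5 | 72–74% | 47–48% |
| 0.7 | 59–60% | 37% |
| 0.9 | 39–40% | 22–23% |

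The first column hardly changes whether the second window is day 14–42 or day 0–42. The second column is for day 14–42 and is a few points lower for day 0–42.

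**After the fix.** With a Benjamini-Hochberg rule at 5% governing the marks, the simulated chance of any false mark falls to about 3–5%.

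**Not counted.** The figures leave out raw concentrations, the second adjustment version, the sex and age strata required by section 14.0, and the within-group marks in Figure 3 (4 groups × 12 readouts × 2 windows = 96).

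**A further open choice.** The list of variables defines fold change from day 0 to days 14 and 42. Section 14.0 and Figure 3 use day 0 to 14 and day 14 to 42. The second window is therefore not settled.

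**The case against.** The strongest reply is that this is a nested mechanistic study with no power claim. Its results are shown as boxplots by group, so an isolated mark would be seen as isolated. The Part B introduction also speaks of exploring BCG. That limits the severity, but it does not answer the wording in section 13.0 or supply the missing rule.

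A reader might go further and infer that a positive finding is the likely result when BCG does nothing. The documents do not support that, for four reasons.

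- The SAP nowhere says that one marked cell establishes trained immunity. Treating any mark as a positive call is a reading imposed on a plan that has no rule.
- Using all 72 tests gives 83–85% at a correlation of 0.5, but 24 of those tests contain no BCG and a mark there could not be credited to it.
- The SAP states no direction, but Figure 3 is described in terms of fold increase. If only increases count, the chance at a correlation of 0.5 is slightly under one half.
- The correlation is assumed, and at 0.9 the two-sided chance among the 48 is about 40%.

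Nor does running adjusted and unadjusted versions double the risk. It gives 144 tests, but these are two views of the same data. Lastly, if Figure 3's mention of bacterial antigens and influenza vaccine leaves out Poly(I:C), the total falls from 72 to 3 × 3 × 2 × 3 = 54. That does not change the conclusion.

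What stands is that the chance of a false mark is several times the nominal 5% in every setting tried, and the plan gives no means of handling it.

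**Conclusion.** The concern holds as a mismatch between claim and method. Forty-eight BCG-containing comparisons per adjustment version are each judged at 0.05, with no lead readout, correction or decision rule, and the SAP says they will determine an answer. With no effect in any arm, at least one mark is expected in about 74% of trials at an assumed readout correlation of 0.5 (88% at 0, 40% at 0.9), or about 47% (66% to 23%) if only increases count. These figures assume normal change scores, a common correlation between readouts and a single adjustment version. It should be corrected, but it concerns a secondary, nested analysis and does not touch the Part B primary outcome.

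**What to change.** - In section 14.0 (Immunological outcomes) and the Figure 3 legend, define the trained-immunity family as the 48 BCG-containing fold-change contrasts in one stated adjustment version. Place the between-group mark only where a Benjamini-Hochberg false discovery rate of 5% across that family is met.
- Reconcile the second window between the list of variables (day 0 to 42) and section 14.0 with Figure 3 (day 14 to 42).
- Unless the sponsor names one deciding readout, window and contrast in advance, label the family exploratory and change *determine whether* in section 13.0 to *explore whether*. The documents do not identify a lead readout, so that choice is the sponsor's.

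The cost is a few lines of SAP text and one line of code, with no new data. The downside is that fewer cytokine differences will be marked as significant.

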**List of variables:**

Variable name	Definition	Type	Scale
Primary outcome: Change in antibody levels to influenza virus strains included in the IIV, comparing levels at day 14 and day 42.			
ab_diff_strain	Influenza antibody titer (GMT) day 42 minus day 14. For each strain.	Continuous	<20 to 320
seroconv	Seroconverted after influenza vaccination (4-fold increase in Ab titer). For each strain.	Binary	0: no 1: yes
Secondary outcome, self-reported infections:			
infection	Infection or symptoms consistent with infection (0 or 1 every survey period).	Binary	0: no 1: yes
Secondary exposure:			
ab_day42_cat	Influenza ab titer day 42 (GMT). Secondary exposure.	Categorical	1. quartile 2. quartile 3. quartile 4. quartile
Secondary outcome, immunological:			
b_lymph	Number of activated B-cells. For all relevant subtypes.	Continuous	0.0-0.3 x 10  /L

cytokine_stim_day	Cytokine concentration (TNF $\alpha$ , IL-1 $\beta$ , IFN- $\gamma$ ) after stimulation with: Poly(I:C), Pam3CSK4, LPS, and influenza vaccine at the various timepoints (day 0, 14, and 42).	Continuous	0-1500 pg/mL
diff_cytokine_stim_day	Fold change in cytokine concentration from baseline value (day 0) to day 14 and 42 after stimulation with various stimuli. Compared between the randomization groups. Using randomization group as exposure (categorical).	Continuous	0-10

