### Objectives and hypothesis

We will test the effects of BCG vaccination on the specific immune response to IIV and on the immune system and health in general in people  $\geq 65$  years, with the aim to:

- Improve their specific antibody response to influenza vaccination.
- Improve their general resistance towards infections.
- Study the effect of BCG on classical lymphocyte-dependent responses, and the induction of innate immune memory.

We will test the following hypotheses:

- a) BCG vaccine given two weeks prior to, together with, or two weeks after IIV is associated with a 30% increase in seroconversion to IIV and/or a significant increase in influenza antibody titers.
- b) The hypothesized potentiating effects of BCG is due to a combination of classical lymphocyte-dependent responses, and the induction of innate immune memory (trained

immunity) in myeloid cells.

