## **13.0 DESCRIPTION OF OUTCOMES AND VARIABLES**

### **Primary outcome**

Change in antibody levels to influenza virus strains included in the IIV, comparing levels at day 14 and day 42; just before and 4 weeks after influenza vaccination (for group 4, it will be 2 and 6 weeks after influenza vaccination).

We will use *Influvactetra* (Mylan ApS, Copenhagen), a quadrivalent inactivated influenza vaccine containing the following strains:

1. A/Victoria/2570/2019, IVR-215 (H1N1, pdm09-like strain)
2. A/Cambodia/e0826360/2020, IVR-224 (H3N2-strain)
3. B/Washington/02/2019, wild type
4. B/Phuket/3073/2013, wild type

Influenza antibodies are measured in hemagglutination-inhibition assay (HAI) yielding dilution titers with an expected range of <20 to 320 for this population. Geometric mean titers (GMT) will be determined by calculating the mean of the log-transformed duplicate titers followed by back transformation (calculated as  $10^x$ , where x is defined as the mean log-transformed titer).

Seroconversion is defined as a pre-vaccination HAI titer <10 and a post-vaccination titer  $\geq 40$ , or a pre-vaccination titer  $\geq 10$  and a minimum four-fold rise in post-vaccination titer.

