### **Secondary outcomes**

*Self-reported infections:*

Infections are identified through information given by the participants in the electronic follow-up questionnaires, where they are asked to describe disease episodes every 14 days. They are asked if they have been ill, and then asked to cross off their symptoms on a list. Furthermore, we ask them to provide the most likely cause for their illness. Disease episodes are characterized as infections if participants report symptoms compatible with an infectious disease or they report an infectious disease diagnose as the cause of their illness. Criteria for self-reported infection:

- Having one or more of the following symptoms: fever, cough, sore throat, runny nose/nasal congestion (common cold symptoms), loss of smell or taste sense, vomiting, or diarrhea with or without general symptoms such as headache, myalgia, dysarthria, or fatigue.
- Having dyspnea AND fever with or without general symptoms such as headache, myalgia, dysarthria, or fatigue.
- Having described an infectious disease as the self-estimated cause of illness. This is a free-text field and participants answers will be classified as infectious disease or not by medically trained study personnel.

Baseline for analysis is set at day 14 reflecting completion of the allocated vaccinations. We will however also conduct the analysis from day 0-14. Participants can register a maximum of one infectious disease event per survey period (14 days).

A secondary analysis of association between influenza antibody level and subsequent risk of infection will be performed to test if high antibody titers correlate with risk of infection.

*Immunological outcomes (subgroup analyses):*

A random subset of participants (the first to accept) have extra blood samples taken for further immunological analyses.

1. Lymphocyte-dependent responses 7 days after influenza vaccination
2. The induction of innate immune memory 14- and 42-days post-randomization

For the lymphocyte analyses, 10 participants from groups 1-3 will have blood drawn on day 21, exactly 7 days after influenza vaccination. We will assess the effect of the different treatment combinations on the response to the influenza vaccine, examining activated

influenza antibody-secreting B-lymphocytes. Due to the different timing of the influenza vaccination, participants from group 4 are not part of this analysis.

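### Part B counts cytokine responses to the trial's own influenza vaccine as trained immunity, although after IIV they may be vaccine-specific recall

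*SAP*

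**What the plan says.** Part B, Objectives and hypothesis, names two mechanisms. Hypothesis (b) holds that the potentiating effect of BCG is "due to a combination of classical lymphocyte-dependent responses, and the induction of innate immune memory (trained" immunity), and places the second mechanism in myeloid cells. Section 13.0, Secondary outcomes, lists them as two numbered immunological outcomes, the second being "The induction of innate immune memory 14- and 42-days post-randomization".

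For that second outcome, "15 participants from each group will have extra blood samples taken on day 0, 14, and 42". PBMCs are stimulated in vitro and three cytokines are measured. The list of variables gives the stimuli: "after stimulation with: Poly(I:C), Pam3CSK4, LPS, and influenza vaccine at the various timepoints". The groups are compared "with and without adjustment for responses in control medium", and the SAP concludes: "This will allow us to determine whether BCG in the different combinations with influenza vaccine induces trained immunity in this population". No stimulus is set apart. Figure 3, titled as the trained-immunity results, is to show "fold increase in cytokine production after stimulation with bacterial antigens and influenza vaccine" together.

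Under Trial design (section 10.0), all participants receive IIV: on day 14 in groups 1 to 3, on day 0 in group 4. For groups 1 to 3, the Primary outcome section describes the day-14 and day-42 samples as "just before and 4 weeks after influenza vaccination".

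**The concern.** One of the four stimuli is the antigen that the trial itself gives between samples. Once a participant has had IIV, the cytokine response of PBMCs to influenza vaccine can include recall by primed lymphocytes, which is the mechanism that hypothesis (b) sets against innate memory. Hypothesis (a) predicts that BCG strengthens the specific response to IIV. If that is true, this readout can rise more with BCG without any change in myeloid cells, and the plan would report the rise as trained immunity. Adjustment for control medium takes out unstimulated background, not antigen-specific recall.

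At stake is the mechanistic conclusion drawn from the subset of 15 per group: an adaptive vaccine response could be published as innate memory induced by BCG.

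**Working it through.** The SAP gives no figure to reproduce here. The check counts the planned contrasts and sets each against the vaccination schedule.

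**Inputs**
- Stimuli: 4; cytokines: 3 (TNFα, IL-1β, IFN-γ). Source: list of variables, section 13.0.
- Intervals: 2 (days 0 to 14, days 14 to 42); comparisons: 3 (groups 1, 3 and 4, each against control group 2). Source: section 14.0, Secondary outcomes.
- Schedule: vaccination table, section 10.0.
- Assumption: blood for this subset is drawn before the day-14 injections, as the Primary outcome section implies for the antibody samples.

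**Counts** (the versions with and without control-medium adjustment are counted once)
- All contrasts: 4 × 3 × 2 × 3 = 72.
- Influenza stimulus: 1 × 3 × 2 × 3 = 18, or 18/72 = 25%.
- Other three stimuli: 3 × 3 × 2 × 3 = 54, or 75%.

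**The 18 influenza-stimulus contrasts** (3 cytokines per cell)

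| Versus group 2 | Days 0 to 14 | Days 14 to 42 |
|---|---|---|
| Group 1 | BCG vs placebo, no IIV yet: 3 not exposed | IIV in both arms, BCG given earlier in group 1: 3 exposed |
| Group 3 | placebo vs placebo, no IIV yet: 3 not exposed | IIV in both arms, BCG added in group 3: 3 exposed |
| Group 4 | IIV vs placebo, no BCG yet: 3 exposed | BCG after earlier IIV vs IIV inside the interval: 3 exposed |

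Exposed, meaning that IIV falls inside the interval for at least one compared group: 9 (days 14 to 42) + 3 (group 4, days 0 to 14) = 12. Not exposed: 6.

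**What the 12 can show**
- Groups 1 and 3, days 14 to 42 (6 contrasts): randomization balances the effect of IIV itself, but not a BCG-boosted recall response. This is where that mechanism applies most cleanly.
- Group 4, days 14 to 42 (3): IIV falls inside the interval only in the control arm, so IIV timing is unbalanced and the direction of any distortion is unclear.
- Group 4, days 0 to 14 (3): IIV against placebo before any BCG. A difference cannot be a BCG effect.

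The list of variables instead defines fold change from day 0 to days 14 and 42. Counted that way, all 9 contrasts over days 0 to 42 contain IIV, and with the same 3 for group 4 over days 0 to 14 the total is again 12.

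**The case against.** The strongest reply is that the damage is contained. The cytokine variables are defined by stimulus and day, with no pooled score, so a reader of Figure 3 can see which result came from which stimulus. The control group also receives IIV. Three of the four stimuli are not influenza antigen, and the lymphocyte mechanism has its own day-21 B-cell readout in groups 1 to 3. All of this is correct and limits the point to one stimulus. It does not answer it: the trained-immunity conclusion is drawn from the whole panel, and no rule says how a rise on the influenza stimulus is to be read. The SAP does see the timing problem for B cells, where it leaves out group 4 because IIV is timed differently, but makes no such provision for cytokines.

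Three stronger readings are tempting, and the document does not support them.
- A reader might infer that the two mechanisms of hypothesis (b) cannot be separated at all. The non-vaccine stimuli, the B-cell readout and the pre-IIV contrast of group 1 with group 2 all remain available.
- A reader might count all 18 influenza-stimulus contrasts as compromised. Six of them precede any trial IIV.
- A reader might want IFN-γ removed for every stimulus as a lymphocyte cytokine. The SAP says nothing about which cells produce it, so that step would rest on outside immunology alone.

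**Conclusion.** The point holds for the influenza stimulus after IIV. There, innate memory cannot be told apart from vaccine-specific recall or its potentiation by BCG, and the plan labels the result trained immunity. This affects 12 of 72 contrasts (12/72 = 17%). Three of the 12 cannot show a BCG effect at all, and the boosted-recall explanation fits most cleanly in 6.

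The conclusion rests on the SAP's own schedule and on one premise that it does not state: that PBMCs contain lymphocytes able to respond to an antigen met before. The counts also assume sampling before injection on day 14. How large a recall response would be is unknown, and no size is claimed.

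This is a secondary outcome in a subgroup. The antibody primary outcome and the infection analysis are untouched, so the change is a cheap improvement and not a condition for the trial's main result.

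**What to change.** In section 13.0 (trained-immunity paragraph), section 14.0 (immunological outcomes) and Figure 3:
- Base the trained-immunity conclusion on Poly(I:C), Pam3CSK4 and LPS, for all three cytokines; IFN-γ can stay. This leaves 54 contrasts.
- Show influenza-vaccine stimulation after IIV in a separate panel, labelled as an antigen-specific or mixed response and not as evidence of trained immunity.
- Keep group 1 versus group 2 over days 0 to 14 for all four stimuli if wished, since it precedes IIV. This would add 3 contrasts.
- State that group 4 versus control over days 0 to 14 reflects IIV and not BCG. That applies to every stimulus, including 9 of the 54 contrasts (3 stimuli × 3 cytokines).

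The cost is SAP wording and one figure panel, with no new samples, assays or change in sample size. The downside is that fewer readouts can support a claim of trained immunity. The wording should be settled before the cytokine results are seen, so that the interpretation is not chosen afterwards.
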